APPROVED BY SALUS IRB: 07 MAY 2024

TITLE: Comparative Study of the DMM and Conventional Toric Marker

PROTOCOL NO: IIT# 92162521

AMENDMENT NO: Version 1.0

IRB: Salus IRB
[name]
[name]

SPONSOR: [name] '[name]

INVESTIGATOR: [name] MD
[name]
[name]
United States

**STUDY-RELATED
[contact] (During business hours)
[contact] (24-Hour line)

1. Executive Summary

NEED

There is currently a paucity of data comparing ARGOS combined with the Digital Marker Microscope and other Conventional Marking Modalities for Toric IOL alignment during cataract surgery.

STUDY OBJECTIVE

To evaluate the postoperative refractive accuracy of the common toric Intraoperative marking method of Toric CAM and Mendez marking when compared to ARGOS combined with the Digital Marker Microscope (DMM)/Vision Suite.

STUDY HYPOTHESIS

The DMM linked to Argos preoperative measurements with limbal registration determines the angle for toric IOL alignment intraoperatively more accurately than the manual Mendez marker.

SUPPORTS CLINICAL MESSAGE

The use of ARGOS with intraoperative image guidance improves the toric alignment error significantly and allows for more % of eyes within 0.5D residual CYL (20% more eyes) as compared to manual marking.

STUDY DESIGN

Sample size	35 eyes
Endpoints	
Primary: Difference in intraoperative axis marks with Mendez marker, in degrees and direction, when compared to the DMM as viewed in the intraoperative heads-up display
 
Secondary: % of eyes less than 0.25, 0.5, 0.75, 1.00 and 1.25 D of residual refractive cylinder (CYL) in each group at 1 month postoperatively

Design:	Single-site, head to head, prospective, interventional (all eyes will be planned/implanted using ARGOS with image guidance axis; and the manual marker results will be back calculated utilizing IOL position and post-operative refraction)
DURATION/FOLLOW-UP:	Preoperative to 1 month postoperative

This study will be registered with clinicaltrials.gov. The study will be conducted in compliance with the protocol, GCP, and applicable regulatory requirements.

2. Study Background

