Toric IOLs offer patients with corneal astigmatism, increased spectacle independence after cataract surgery. Toric marking aims at improving the accuracy of incision location and IOL alignment. Conventional markers rely on a reference mark tied to gravitational alignment and the accuracy in manual marking methods is affected by head position, errors on marking and smearing of ink. Digital marking methods aim to reduce intraoperative IOL misalignment using images captured in the sitting position which are used as overlay for IOL alignment intraoperatively¹. The DMM linked to ARGOS preoperative measurements with limbal registration determines the exact angle for toric IOL alignment intraoperatively.

The purpose of this study is to compare the outcome of toric IOL implantation guided by manual or digital marking techniques. The intrinsic difference in the toric axis alignment may lead to a significant difference in the marked alignment axis intraoperatively resulting in superior refractive outcomes and less residual astigmatism using intraoperative alignment from the ARGOS Vision planner and DMM.

3. Study Design

- A single site, interventional study comparing the ARGOS/ DMM axis to the Mendez toric marker paired with the toriCAM smart phone app.
- There will be 35 eyes total that meet the inclusion criteria. Patient's refraction will be evaluated 4 weeks after cataract surgery with a monofocal toric IOL (Clareon Toric).
- Intraoperative difference in toric marks will be recorded in degrees and direction of marking difference (clockwise and counterclockwise).
- Post operative refraction will be obtained at 4 weeks after surgery using standard Snellen acuity chart and phoropter. IOL position will be verified with slit lamp photography aligned with preoperative Argos toric imaging to ensure that IOL position is NOT a source of refractive error.
- We will perform back calculation of theoretical refraction, as if the IOL was positioned at Mendez marking axis rather than the Argos axis. This will be calculated using the IOL position and post operative refraction with Astigmatismfix.com calculator or equivalent calculator

4. Study Inclusion and Exclusion Criteria

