5.2 Operative (Day of Surgery)

All subjects will undergo femto-second assisted cataract surgery with implantation of the Clareon monofocal toric IOL.

The toriCAM smartphone app will be used to mark the horizontal axis as a reference preoperatively in a sitting position. The target axis of the IOL, as calculated by the Argos, will be marked intraoperatively with a Mendez marker based on the horizontal reference marker from the Toric Cam.

After phacoemulsification, the Digital Marker Microscope (DMM) will be used to determine the target axis by using an image overlay

The difference in the final marked IOL axis and the DMM axis will be measured using the DMM degree overlay intraoperatively. The difference in degrees and the direction will be recorded.

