5.3 Postoperative Visits

Subjects will undergo all routine, usual standard-of-care postoperative procedures and follow up appointments.

In addition, 4 weeks following cataract surgery, the final position of the IOL will be confirmed using a slit lamp photograph compared to the ORIGINAL Argos reference image. The surgeon will confirm that the IOL is within 2 degrees of the final intended axis as calculated by the Alcon Vision Planner.

Then the postoperative subjective refraction shall be measured by Snellen and Phoropter method and the theoretical refraction shall be back calculated using the double vector method to arrive with the refraction that would have been obtained by the Mendez marking

method. This will be calculated using the IOL position and post operative refraction with Astigmatismfix.com calculator or equivalent calculation.

6. Statistical Analysis

A summary of the data will be prepared for all measurements. For variables measured on a continuous scale, these summaries will include the sample size, as well as the mean, standard deviation, median, minimum, and maximum. For variables measured on a categorical scale, summaries will provide the number and percentage of eyes in each category. These summaries will be provided for all eyes completing the study.

The statistical analyses will be performed using R, version 4.2.2 or higher. Any statistical tests of hypotheses will employ a level of significance of alpha=0.05.

The primary endpoint will be compared using the paired t-Test. Secondary endpoints will be compared using McNemar's test. Analysis will follow a step down approach:

- Difference in intraoperative axis marks with Mendez marker, in degrees and direction, when compared to the DMM viewed in the intraoperative HUD
- % of eyes less than 0.5D CYL in each group
- % of eyes less than 0.25D CYL in each group
- % of eyes less than 0.75D CYL in each group
- % of eyes less than 1.0D CYL in each group
- % of eyes less than 1.25D CYL in each group

7. Sample Size Justification

Based on the primary endpoint, the study would require a sample size of 21 pairs (to achieve a power of 80% and a level of significance of 5% (two sided), for detecting a mean of the differences of 4.4 between pairs, assuming the standard deviation of the differences to be 6.5.¹

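### The primary t-test measures disagreement between the Mendez mark and the DMM axis; it cannot test the hypothesis that the DMM is more accurate

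*Combined protocol and SAP*

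**What the plan says.** The Study Hypothesis in section 1 is comparative: the DMM "determines the angle for toric IOL alignment intraoperatively more accurately than the manual Mendez marker". The clinical message in the same section is that image guidance "improves the toric alignment error significantly".

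The primary endpoint in section 1 is "Difference in intraoperative axis marks with Mendez marker, in degrees and direction, when compared to the DMM as viewed in the intraoperative heads-up display". Section 3 has the direction recorded as clockwise or counterclockwise. Section 5.2 describes the measurement: "The difference in the final marked IOL axis and the DMM axis will be measured using the DMM degree overlay intraoperatively".

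Section 6 gives the analysis: "The primary endpoint will be compared using the paired t-Test". It adds that "Analysis will follow a step down approach", with the axis difference first and five residual-cylinder comparisons after it. Section 7 sizes the primary endpoint "for detecting a mean of the differences of 4.4 between pairs, assuming the standard deviation of the differences to be 6.5", two-sided 5%, 80% power, 21 pairs. The secondary calculation gives 30, raised to 35 eyes for dropout.

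The plan gives no sign convention, null value or direction of benefit for the primary test. It defines no independent axis against which each marker's error would be scored.

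**The concern.** A claim that one marker is more accurate needs each marker's error against a common reference. Here one marker is the reference. Any error in the DMM is therefore booked as Mendez error, and a significant result says only that the two differ.

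There is a second problem if the sign is kept. A t-test then asks whether the mean rotation is zero. A Mendez marker that scatters widely but evenly in both directions would usually pass, while one with a small consistent offset would fail.

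What is at stake is the reading of the result. A significant primary test would invite the conclusion already written into the hypothesis and the clinical message, which that test cannot support. A non-significant one could be read as showing that manual marking is adequate when the scatter is large.

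**Working it through.** **Inputs from the documents.** Mean difference 4.4 and SD 6.5 (section 7; no unit given, taken as degrees), two-sided 5%, 80% power, 21 pairs, 30 eyes before dropout and 35 planned.

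**Step 1: the plan's own figure.** Normal approximation: n = (SD × (z₀.₉₇₅ + z₀.₈₀) / δ)² = (6.5 × (1.960 + 0.842) / 4.4)² = 17.1. Adding z₀.₉₇₅²/2 = 1.92 for the t-test gives 19.05, so 20. By exact noncentral t, power is 79.7% at n = 19, 81.9% at 20 and 83.9% at 21. The stated 21 is about right. It is power to detect a non-zero mean difference, and nothing else.

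**Step 2: which marker is wrong?** Write e_M and e_D for the errors of the Mendez mark and the DMM axis against the unknown true axis. The trial observes only D = e_M − e_D. At n = 30 the noncentrality is √30 × 4.4/6.5 = 3.71, and power is 94.8% however the error is divided. Simulation (normal errors; the division between markers is assumed):

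| Source of the error, n = 30 | Rejection |
|---|---|
| All Mendez: mean 4.4, SD 6.5; DMM exact | 95% |
| All DMM: mean −4.4, SD 6.5; Mendez exact | 95% |
| Shared: means ±2.2, SD 4.6 each (mean absolute error 4.1 degrees for both) | 95% |
| DMM biased by 4.4, Mendez unbiased, SD 4.6 each (Mendez better by about 1.6 degrees in mean absolute error) | 95% |

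The last row is a trial in which the hypothesis is false and the test still rejects.

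**Step 3: signed reading.** For a normal difference with mean μ, the mean absolute value is SD√(2/π)·exp(−μ²/2SD²) + μ(1 − 2Φ(−μ/SD)). Rejection is by exact noncentral t, n = 30:

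| Mean / SD of difference | Mean absolute difference | Rejection |
|---|---|---|
| 0 / 6.5 | 5.2 degrees | 5% |
| 4.4 / 6.5 | 6.3 degrees | 95% |
| 1 / 1.5 | 1.45 degrees | 94% |

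With the mean absolute difference held at 4.4 degrees (half-normal sizes, random direction), rejection is 5% at a 50:50 direction split, 44% at 70:30 and 81% at 80:20. The result follows the balance of directions, not the size of the misalignment. If the DMM is truly better and neither marker is biased (assumed SDs of 2 and 6.18, giving 6.5 for the difference), rejection is again about 5%.

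**Step 4: unsigned reading.** An absolute difference cannot be negative, so its mean exceeds zero unless the two markers agree exactly in every eye. Tested against zero, it rejected in essentially all of 40,000 simulated trials at n = 21, 30 and 35, even with no bias and a difference SD of 1 degree (mean absolute 0.8 degrees).

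**Step 5: precision of the proposed quantity.** The SD of the absolute difference is √(μ² + SD² − (mean absolute)²): 3.92 at 0/6.5 and 4.64 at 4.4/6.5. At 30 eyes the 95% half-width is 1.96 × 3.92/√30 = 1.40 and 1.96 × 4.64/√30 = 1.66. With the t multiplier of 2.045 these become 1.46 and 1.73. So it is about 1.4 to 1.7 degrees.

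**The case against.** **The plan never says that the t-test uses signed values.** This stands. Recording direction and powering on a mean of differences make the signed reading natural, but section 6 does not commit to it. The sample-size inputs do not settle it either: a zero-centred normal difference with mean absolute value 4.4 would have an SD of absolute values near 3.3, not 6.5. The cancellation argument is therefore conditional. The reference argument in step 2 is not.

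**The trial does contain evidence on accuracy.** This also stands. Refraction is measured with the lens at the image-guided axis and back-calculated for the Mendez axis. If the DMM axis were the wrong one, the back-calculated cylinder could favour Mendez. A reader might infer that these data cannot address accuracy at all; the documents do not support that.

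**The scatter will be visible anyway.** Section 6 requires the SD, median, minimum and maximum of continuous measurements, so wide symmetric scatter would be reported. That reduces the harm but does not repair the test.

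**The week-4 photograph checks the DMM.** It compares the lens with the Argos reference image and the planned axis. It does not score the Mendez and DMM marks against an independent axis.

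**Failure of the primary test would block the cylinder comparisons.** This stronger reading is tempting, but it needs a strict gate, and no stopping rule is written. It also needs a mean near zero, whereas the plan assumes 4.4, at which the signed test rejects 95% of the time at 30 eyes.

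**Conclusion.** The concern holds for the primary test and for claims drawn from it. On either reading, that test can show disagreement with the DMM and cannot show that the DMM is more accurate. The reference problem rests only on the endpoint definition in sections 1, 3 and 5.2. Its size is that rejection is 95% at 4.4/6.5 and 30 eyes, whichever marker carries the error.

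The cancellation problem (5% rejection with 5.2 degrees of average disagreement) further assumes signed analysis, normal differences and a mean near zero, which is not the plan's assumption. The divisions of error between markers and the direction splits are illustrative. The residual-cylinder comparison is outside this criticism.

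**What to change.** 1. In sections 1 and 6, define the primary quantity as the mean absolute Mendez–DMM axis difference (0 to 90 degrees, with wrap at 180) and give a 95% CI. Report the signed mean with 95% limits of agreement beside it.
2. Word the hypothesis and conclusion for this endpoint as disagreement with the DMM. Rest any accuracy claim on the residual-cylinder comparison.
3. Do not test the absolute difference against zero. A test against a non-zero margin justified by the sponsor is optional. It would still not rank the markers: two equally accurate ones (SD 3 degrees each) exceed an illustrative 2-degree margin in 87% of simulated trials.
4. If no axis test is kept, state which cylinder comparison opens the step-down. Restate the section 7 basis for the primary endpoint as CI precision: a half-width of about 1.4 to 1.7 degrees at 30 eyes, under a difference SD of 6.5 and a signed mean of 0 to 4.4.

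The cost is a protocol amendment and a weaker claim for the primary endpoint. No new measurement and no additional eyes are needed.

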However, in order to achieve a sample size that allows for statistical analysis of the secondary endpoints, we estimate the sample size required for detecting a difference of 0.20 between the percentage of with postoperative residual astigmatism 0.5 D or less (85% compared to 65%), power of 85%, correlation between paired observations 0.80, and a two-sided significance of 5% is 30.²

To account for dropout, the sample size will be increased to 35 eyes.

References

1. Lipsky L, et al. Comparison of toric intraocular lens alignment error with different toric markers. *J Cataract Refract Surg.* 2019; 45:1597–1601.

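### Residual cylinder is tested only as percentages under cut-offs whose inequality differs between Sections 6 and 7, and the paired dioptre values get no test or confidence interval

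*Combined protocol and SAP*

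**What the plan says.** Section 1 gives postoperative refractive accuracy as the objective. Its secondary endpoint is the percentage of eyes under 0.25, 0.5, 0.75, 1.00 and 1.25 D of residual cylinder.

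Section 6 says "Secondary endpoints will be compared using McNemar"'s test, and lists the 0.5 D item first among the five as the percentage "of eyes less than 0.5D CYL in each group". The paired t-test is reserved for the axis difference in degrees. Continuous variables receive descriptive summaries only. Tests use a "level of significance of alpha=0.05".

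Section 7 sizes the secondary comparison on "postoperative residual astigmatism 0.5 D or less" ("85% compared to 65"%, "correlation between paired observations 0.80", power 85%), and the requirement with "a two-sided significance of 5% is 30". The clinical message in Section 1 uses a third wording, eyes inside 0.5 D.

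Section 5.3 says that "the postoperative subjective refraction shall be measured by Snellen and Phoropter method", and that the Mendez refraction is then calculated from it. Every completed eye therefore has two cylinder values in dioptres.

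**The concern.** Two separate things are at stake.

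**Sensitivity.** Turning two dioptre values into a yes/no pair discards how far each lies from the cut-off. With about 30 eyes, only the few that cross the cut-off contribute to McNemar's test. A real refractive difference could go undetected although the data to show it were collected.

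**Cut-off definition.** Sections 6 and 7 disagree on whether an eye at exactly 0.50 D counts as a success. All five cut-offs are multiples of 0.25 D. If the phoropter value moves in 0.25 D steps, many DMM eyes can sit exactly on a cut-off, while an unrounded calculated Mendez value almost never will. The inequality then treats the two arms differently.

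**Working it through.** **1. The plan's own figure of 30.** Inputs from Section 7: p1 = 0.85, p2 = 0.65, d = 0.20, correlation 0.80, power 85%, two-sided 5%.

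- Both-success cell: p11 = p1·p2 + φ·√[p1(1−p1)p2(1−p2)] = 0.5525 + 0.80 × 0.1703 = 0.6888.
- Mendez-only success: 0.65 − 0.6888 = −0.039, which is impossible. The largest feasible φ is (0.65 − 0.5525)/0.1703 = 0.57.
- Formula: n = [1.96√pd + 1.036√(pd − d²)]²/d², where pd is the discordant proportion.
- At φ = 0.80, entered mechanically, pd = 0.1225 and n = (0.686 + 0.298)²/0.04 = 24.2, so 25. A half-unit continuity correction gives 29-30. The stated 30 is reached only that way, from inputs that no data set can have.
- At φ = 0.57, pd = 0.20 and n = (0.877 + 0.415)²/0.04 = 41.7, so 42. Power at n=30 is 57% exact or 88% uncorrected.

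The impossible correlation is a separate defect. It matters here because the plan gives no usable within-pair correlation.

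**2. Power, McNemar against a paired t-test, unrounded values.**

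- From Section 7: mark difference mean 4.4, SD 6.5 degrees, treated as a signed normal rotation.
- Assumed: lens cylinder 1.25 D; DMM residual bivariate normal in double-angle space, SD 0.25 to 0.257 D per axis; lens error either none or uniform within the 2 degrees allowed by Section 4.2.
- Calibration: P(cylinder ≤ 0.5) = 1 − exp(−0.5²/2s²). For s = 0.257 this is 1 − exp(−1.893) = 85%; for s = 0.25 it is 86%.
- Mendez cylinder: the length of the DMM residual vector plus the vector produced by rotating the lens. This gives about 65% at 0.5 D, a mean increase of about 0.11 D and an SD of 0.21 D.

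| Setting | McNemar exact | McNemar uncorrected | Paired t |
|---|---|---|---|
| 1.25 D, n=30 (about 85% v 65%) | 42-47% | 56-61% | 82-86% |
| 1.25 D, n=35 | 51-53% | 63-66% | 88-90% |
| 1.0 D, n=30 | 22% | 40% | 65% |
| 1.5 D, n=30 (about 86% v 60%) | 61-62% | 72-73% | 92% |
| 2.0 D, n=30 | 85% | 90% | 99% |

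Only the 1.25 D rows match the plan's rates; the others show sensitivity to lens power. A simpler bivariate-normal model, fixed at 85% v 65% with cylinder correlation 0.3 to 0.9, gives exact McNemar 36-55%, uncorrected 46-82%, and paired t 83% to over 99% at n=30.

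**3. The inequality, with stepped refraction.** This is a different data model. DMM cylinder is rounded to 0.25 D (assumed), Mendez is calculated from it and left unrounded, with a 1.25 D lens and n=30.

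- DMM eyes recorded at 0.50 D are those with true cylinder from 0.375 to 0.625 D. With s = 0.257 the share is exp(−1.065) − exp(−2.957) = 0.345 − 0.052 = 29%.
- Hence DMM is 1 − 0.345 = 65.5% under < and 1 − 0.052 = 94.8% under ≤. With s = 0.25 and the lens error included, the figures are about 67% and 95%.

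| Mark difference | < 0.5 D, DMM v Mendez | ≤ 0.5 D, DMM v Mendez |
|---|---|---|
| mean 4.4, SD 6.5 degrees | 67% v 65%, exact power about 2% | 95% v 65%, exact power about 91% |
| mean 0, SD 0.5 degrees | 67% v 81% (favours Mendez) | 95% v 81% (favours DMM) |

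The paired t-test stays near 85% in the first row. In the second row mean cylinder is about 0.322 v 0.324 D, so neither percentage difference is real. The dioptre test is not wholly immune. With a 1.5 D lens and a mark difference of SD 1 degree, it rejected in 15% of runs (8% unrounded), for a mean change of only 0.007 D.

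**4. Rounding both values.** The spurious difference in step 3 disappears. At mean 4.4, SD 6.5 degrees, exact McNemar power is about 43% (<) or 32% (≤), against 82% for the paired t-test. The sensitivity gap therefore remains.

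**The case against.** The plan's claim is a percentage, the study is sized on percentages, and McNemar's test is right for paired percentages. A dioptre comparison answers a different question: its expected difference, about 0.11 D, is under half of an assumed 0.25 D step and would not establish a 20-point gain. The dioptre values are already summarised descriptively, and these are secondary endpoints. All of that stands.

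The size of the loss rests on inputs absent from the documents. At the largest feasible correlation, uncorrected McNemar reaches 88% at n=30, and the plan does not say which version it will use. This also stands, although the exact version gives only 57% there.

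Three stronger readings are tempting. A reader might infer that the planned test is invalid; it is not. A reader might infer that the inequality will reverse the result. The reversal appears only with a negligible mark difference; at 4.4/6.5 degrees, < removes the contrast without reversing it. Either effect also needs a refraction step and an unrounded calculator output, and the documents state neither. A reader might also combine the power figures with the artefact figures. They come from incompatible data models, one unrounded and one stepped, and cannot both apply.

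What survives without any assumption is that Sections 6 and 7 define the 0.5 D endpoint differently, and that no paired inference in dioptres is planned.

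**Conclusion.** The point holds as an improvement that should be made, not as an invalid analysis. The conflict between < and ≤ is visible in the text. The loss of sensitivity had the same direction at every lens power tried. At about 85% v 65%, n=30 and an assumed 1.25 D lens, exact McNemar has roughly half the power of a paired t-test, and the gap varies with lens power and within-pair correlation. The inequality effect is conditional on 0.25 D steps and an unrounded Mendez value. Under those conditions it moves the 0.5 D contrast from about 2 points to about 30, and exact power from about 2% to about 91%.

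A dioptre test does not cure the built-in asymmetry of the design: every lens sits at the DMM axis, eyes more than 2 degrees off are excluded, and the Mendez result is theoretical.

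**What to change.** Before any outcome data are examined:

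1. Use one inequality for the cylinder cut-offs in Sections 1, 6 and 7.
2. State the refraction step, and round the back-calculated Mendez cylinder to that step before applying any cut-off.
3. Add to Section 6 a prespecified paired comparison of residual cylinder in dioptres, DMM minus Mendez: mean difference with 95% CI, paired t-test, and signed-rank test as a check. Make it supportive, alongside or directly after the 0.5 D test. Placing it earlier would make the endpoint on which the study was sized depend on a new test.
4. State which version of McNemar's test will be used (exact, corrected or uncorrected), because the power figures differ materially between them.

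The cost is a few lines of text and one more analysis; no extra eyes, visits or measurements are needed. The dioptre result would not by itself support the 20-point percentage claim, and the report should say so.

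### Section 6 names McNemar's test without a version; at the expected 6 to 9 discordant eyes the version can decide significance, and only one version in one scenario reaches the stated 85% power at 30 eyes

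*Combined protocol and SAP*

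**What the plan says.** Section 6 (Statistical Analysis) gives the test for the percentages of eyes under each cylinder cut-off in one sentence: "Secondary endpoints will be compared using McNemar's test". On software it says "The statistical analyses will be performed using R, version 4.2.2 or higher", and on level "Any statistical tests of hypotheses will employ a level of significance of alpha=0.05". No version of the test, R function or option is named there or elsewhere. The endpoints are tested in a step-down order, with the 0.5 D cut-off first after the primary endpoint.

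Section 7 (Sample Size Justification) sizes the trial on that 0.5 D comparison, for "detecting a difference of 0.20 between the percentage of with postoperative residual astigmatism 0.5 D or less" at rates of 85% and 65%, with "power of 85%, correlation between paired observations 0.80, and a two-sided significance of 5% is 30". It then adds: "To account for dropout, the sample size will be increased to 35 eyes". It gives no discordant rate or count.

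**The concern.** McNemar's test uses only the discordant eyes, those within 0.5 D under one marking method and not under the other. With few such eyes the four common versions (uncorrected, continuity-corrected, exact and mid-p) have clearly different rejection rules. Two things follow.

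- **The verdict may depend on a choice the plan leaves open.** That choice could be made after the data are seen, at the comparison that set the sample size. If the step-down is a fixed sequence, this comparison also decides whether the other four cut-offs are tested.
- **The stated power is not tied to a test.** The 85% in Section 7 cannot be checked against the analysis until a version is named, and most versions fall well short of it.

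**Working it through.** **Inputs.** From Section 7: rates 0.85 and 0.65, difference d = 0.20, two-sided 5%, power 85%, correlation 0.80, 30 evaluable eyes, 35 enrolled. From Section 6: McNemar's test, alpha 0.05. Assumed, because the plan is silent: the split of discordant eyes.

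**The plan's own figure.** Use n = [z(α/2)·√pd + z(β)·√(pd − d²)]² / d², where pd is the discordant share. Taking correlation 0.80 literally gives pd = 0.1225 and n = 24.2, so 25 eyes. Adding 1/d = 5 gives 29.2, so 30; a Fleiss-type correction gives 28.98, so 29. Of these, only the formula with 1/d added gives 30. The inputs are not feasible, however. The largest correlation these rates allow is (0.65 − 0.65×0.85)/√(0.65×0.35×0.85×0.15) = 0.572, and pd cannot be below 0.85 − 0.65 = 0.20.

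**Expected discordant eyes.** Write p10 for the share within 0.5 D only under the digital axis and p01 for the reverse. Three feasible cases keep the 20-point difference: 20%/0%, 22.5%/2.5% and 25%/5%. They give 30×0.20 = 6, 30×0.25 = 7.5 and 30×0.30 = 9 discordant eyes.

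**P-values by version.** With b and c the two discordant counts:
- uncorrected: χ² = (b−c)²/(b+c)
- corrected: χ² = (|b−c|−1)²/(b+c)
- exact: 2·P(X ≤ min(b,c)), with X ~ Binomial(b+c, ½)
- mid-p: exact minus P(X = min(b,c))

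For 4 v 0: χ² = 16/4 = 4.00 uncorrected and 9/4 = 2.25 corrected; exact 2/16 = 0.125; mid-p 0.125 − 0.0625 = 0.0625.

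| Split | Uncorrected | Mid-p | Exact | Corrected |
|---|---|---|---|---|
| 4 v 0 | 0.046 | 0.063 | 0.125 | 0.134 |
| 5 v 0 | 0.025 | 0.031 | 0.063 | 0.074 |
| 6 v 0 | 0.014 | 0.016 | 0.031 | 0.041 |
| 7 v 1 | 0.034 | 0.039 | 0.070 | 0.077 |
| 9 v 2 | 0.035 | 0.039 | 0.065 | 0.070 |

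**Power.** Exact enumeration: discordant count m ~ Binomial(n, p10+p01), then b given m ~ Binomial(m, p10/(p10+p01)), with each rule applied at two-sided 0.05. In the 20%/0% case at n = 30 the uncorrected test rejects at m ≥ 4 (0.877), mid-p at m ≥ 5 (0.745) and exact or corrected at m ≥ 6 (0.572).

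| n | p10/p01 | Corrected or exact | Mid-p | Uncorrected | Corrected and uncorrected disagree |
|---|---|---|---|---|---|
| 30 | 20/0 | 57% | 74% | 88% | 30% |
| 30 | 22.5/2.5 | 48% | 61% | 65% | 17% |
| 30 | 25/5 | 40% | 52% | 53% | 12% |
| 35 | 20/0 | 73% | 86% | 94% | 21% |
| 35 | 22.5/2.5 | 59% | 70% | 72% | 13% |
| 35 | 25/5 | 49% | 59% | 60% | 11% |

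The rows for 35 assume no dropout.

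**True level.** The same enumeration with p10 = p01, at n = 30:

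| Null discordance | Corrected or exact | Mid-p | Uncorrected |
|---|---|---|---|
| 20% | 1.3% | 3.1% | 4.8% |
| 25% | 1.8% | 3.7% | 4.5% |
| 30% | 2.1% | 4.0% | 4.3% |
| Maximum over 2% to 80% | 2.9% corrected, 3.0% exact | 4.8% | 5.4% |

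These levels are averages over a random discordant count. Given exactly 6 discordant eyes, every version rejects only at 6 v 0 and has level 2/64 = 3.1%.

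**The case against.** **R's default settles the version.** A reader might infer that naming R means the continuity-corrected form, and the 30 eyes are matched only with a correction term added. But the plan names no function, R's default is an outside assumption, and the match rests on a correlation that cannot occur. If the corrected form is nevertheless what was meant, the ambiguity goes but the power is 40% to 57% at 30 eyes, so the Section 7 figure still needs correcting.

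**Conservative versions are safe, and exact is a legitimate choice.** This stands. The exact test guarantees 5% control and mid-p does not. It would be wrong to say that the exact form gives up power for nothing; preferring mid-p is a judgement about that trade.

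**The largest gaps come from the most favourable case.** This stands too. The 88% v 57% contrast and the 30% disagreement need no eye to do better under Mendez marking. With 5% reverse changes, disagreement is 12% at 30 eyes.

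**The real fault is the correlation.** The 0.80 is a separate Section 7 error. Correcting it leaves Section 6 silent on the version. Equally, the size of the problem is not independent of the correlation, because correlation fixes the discordance: the mid-p gain is 17 points at 20% discordance and 11 at 30%.

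**These are secondary endpoints.** True, and the primary paired t-test is untouched. But this comparison raised the requirement from 21 pairs to 30.

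**Conclusion.** The point holds. Section 6 leaves open a choice that would change the 0.5 D verdict in roughly one trial in eight to one in three at 30 eyes. The 85% power at 30 eyes is reached only by the uncorrected test with no reverse changes. The corrected or exact form falls short at 30 eyes, and even at 35, in every feasible case examined.

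Two stronger readings are not supported. A reader might infer serious type I error inflation from the open choice; but the corrected, exact and mid-p forms stay below 5% over the range checked, and the uncorrected form, which gives the smallest p-value in every split tabulated, peaks at 5.4%. A reader might also infer that mid-p repairs the power; it reaches only 52% to 74% at 30 eyes, and passes 85% at 35 only with no reverse changes and no dropout.

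The figures rest on the planned 85% and 65%, the three assumed discordance splits, and a null discordance of 20% to 30% for the quoted levels. The plan states none of the discordance values.

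**What to change.** **Section 6.** Before data are available, name one version for all five cut-offs, with the R function and option or the code. Preferred: the two-sided mid-p McNemar test, computed from the binomial distribution on discordant eyes. At 30 eyes it gains 11 to 17 points over the corrected or exact form, with a level of at most 4.8% over 2% to 80% discordance. If guaranteed 5% control matters more, the exact test also removes the ambiguity, at 40% to 57% power with 30 eyes and 49% to 73% with 35.

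**Section 7.** Restate power for the named test under feasible discordance. For mid-p this is about 52% to 74% at 30 evaluable eyes and 59% to 86% at 35. The 0.80 correlation must be corrected separately.

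**Cost.** One sentence in Section 6, a few lines of R, and a revised power statement; no extra eyes or procedures. The downsides are that mid-p has no strict 5% guarantee and that the stated power will be visibly lower than 85% at 30 eyes.
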